## 11.6 Other Safety Measures

### 11.6.1 Vital Signs

The following summaries will be provided by groups defined in Section 11:

- Values of vital signs by scheduled visit
- Change from reference visit by scheduled visit

### 11.6.2 Electrocardiograms (ECG)

Shift tables will be presented by groups defined in Section 11. They will give the n (%) of subjects who shift from Screening to Week 53 among the following categories:

- Normal
- Abnormal

### 11.6.3 Physical Examination

At Screening, all clinically significant abnormal findings are reported on the Medical History form. For all other visits, all new clinically significant abnormal findings or clinically significant deteriorations are reported on the Adverse Events form.

### 11.6.4 Hemolysis

Clinical hemolysis will be considered based on criteria given in Section 8 of the Clinical Study Protocol as:

***Confirmed hemolysis:***

Subjects fulfilling criterion A and at least 2 of criteria B, where 1 of the minor criteria must be direct antiglobulin test (DAT) positive after infusion and within 28 days of the first IMP infusion, will be considered to have “confirmed hemolysis.” Confirmed hemolysis will be reported as an AE.

***Suspected hemolysis:***

Subjects fulfilling criterion A and at least 1 of criteria B will be considered to have “suspected hemolysis.”

- Criterion A
  - Drop in hemoglobin of  $> 1$  g/dL since the time of first administration of IMP without clinical evidence of blood loss from gastrointestinal bleeding, menorrhagia, hemoptysis, major hematoma, or injury and not explained by repeated phlebotomy
- Criteria B
  - Presence of minor criteria documented since the time of first administration of IMP, consisting of:
    - DAT positive
    - Haptoglobin  $<$  lower limit of normal
    - LDH  $>$  ULN
    - Total or indirect (unconjugated) bilirubin  $>$  ULN or jaundiced
    - Hemoglobinuria or red/dark urine

- Hemoglobinuria
- Hemoglobinemia
- Spherocytosis
- Hepatosplenomegaly

Hemoglobinuria, hemoglobinemia and hepatosplenomegaly will be assessed by medical review, if no clinical signs occur these criteria will be disregarded.

Hemolysis findings will be analyzed descriptively, displaying number of subjects and percentage.

### **11.6.5 Wells' Criteria Score**

Data for Wells' criteria Score for deep vein thrombosis (DVT) and pulmonary embolism (PE) will be analyzed descriptively.

## **12 Pharmacokinetic Analyses**

Serum samples for IgG level determination will be collected at Screening and at specified study visits.

Additional blood samples for rich PK sampling of IgG levels will be collected at Week 37 on up to 10 Japanese subjects and 30 non-Japanese subjects.

All non-compartmental analyses are to be performed according to PK-GDL-01.

The merge of PK concentration data and eCRF data to generate a data set with actual blood sampling times, actual sampling time relative to the start of the dose infusion, actual infusion durations, actual dose and PK concentrations, along with derivation of PK parameters will be performed after database lock by CSL Behring or their designate.

### **12.1 Drug Concentration Measures**

IgG concentrations from rich PK sampling will be listed for individual subjects and summarized by nominal (planned) time points and by region (Japan vs non-Japan). Individual concentration-time profiles and mean ( $\pm$  standard deviation) profiles will be plotted using actual time points for individual plots and nominal (planned) time points for mean profiles on both log-linear and linear scales. Mean profiles will be provided overall and stratified by dosing regimen (1, 2, 3, or

---

4-day administration) at Week 37 (ie, week of rich PK sampling) and region (Japan vs non-Japan).

Serum IgG levels other than the rich PK sampling will be summarized by visit, treatment sequence, period, and region (Japan vs non-Japan), separately from the rich PK summaries.

## 12.2 Deriving and Summarizing Pharmacokinetic Parameters

Non-compartmental PK analysis will be performed by CSL Behring or its designate for PK parameter derivation using Phoenix WinNonlin, Version 6.3 or higher. Only concentrations from rich PK sampling will be used to calculate the PK parameters based on the PK analysis set. The following PK parameters will be derived using actual sampling collection times:

AUC 0-tau	Area Under the serum concentration-time Curve from time-point zero (Day 1) through tau=Day 7 (at Week 37), calculated using a combined linear and logarithmic trapezoidal rule (linear up-log down).
C trough	Trough concentration in serum, collected prior to the next infusion during a treatment regimen.
C max	Maximum observed concentration in serum.
T max	Time to reach C max
C ss/F	Apparent clearance at steady state
V z,ss/F	Apparent volume of distribution of the terminal phase at steady state

The plasma PK parameters will be listed and summarized with the following: n, mean, SD, geometric mean, geometric % CV, median, first quartile, third quartile, minimum, and maximum for all PK parameters except tmax. Tmax will be summarized with n, minimum, median, first quartile, third quartile and maximum. Summary statistics will be grouped by dosing regimen (1, 2, 3, or 4-day administration) and region (Japan vs. non-Japan).

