### 3.3.2 Dose Rationale

The few small studies that have utilized SCIG for treatment in patients with DM/PM relied on precedence from IVIG dosing to determine optimal SCIG dosing. From the first study in 1987 in a single subject with PM, to the Dalakas 1993 study and 2 Japanese studies, a 2 g/kg body weight per month IVIG dose was used as a standard dose in treatment of subjects with DM/PM [Dalakas, 1991; Dalakas et al, 1993; Saito et al, 2008; Miyasaka et al, 2012], and has been commonly adopted in clinical practice and standard of care. In smaller, open-label studies, similar SCIG monthly doses were used (2 g/kg body weight [Danieli et al, 2011; Gelardi et al, 2014], 1.9 g/kg body weight [Cherin et al, 2016], and 1.7 g/kg body weight [Schleinitz et al, 2008]) in subjects with DM/PM. In these studies, the standard IVIG dose for subjects with DM/PM was divided into weekly SCIG doses approximately equivalent to 0.5 g/kg body weight per week. Positive responses were noted as early as 3 months (the earliest tested time points for improvement). In addition, CSLB performed a simulation using a previously developed population PK model based on data from subjects with CIDP (mechanism of action postulated to be immunomodulatory) to assess in subjects with DM, predicted IgG exposure after treatment with a 0.5 g/kg SC dose of IgPro20. These analyses predicted that the median average concentration estimated as area under the concentration-time curve for a specific time interval ( $AUC_{0\text{-time}}$ )/dosing interval was comparable following 2 g/kg monthly IVIG (22.20 g/L) and 0.5 g/kg weekly SCIG (20.85 g/L), after 8 to 10 weeks. The analysis also predicted trough concentration ( $C_{\text{trough}}$ ) at steady state, which appears to be higher for 0.5 g/kg weekly SCIG (17.12 g/L) compared to 2 g/kg monthly IVIG (13.15 g/L). The higher  $C_{\text{trough}}$  following 0.5 g/kg SCIG dose is likely due to a shorter dosing interval following weekly dosing. Overall, this analysis provides evidence of comparable steady-state IgG exposure after SC dosing of 0.5 g/kg body weight weekly and IV dosing of 2 g/kg body weight monthly. Based on the clinical evidence and outcome of the simulations, we have chosen 0.5 g/kg body weight as the weekly IgPro20 dose in this study.

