## 5 Study Interventions

### 5.1 Investigational Products

#### 5.1.1 Description of IgPro20

Substance name	IgPro20
Active substance	Human normal IgG
Trade name	Hizentra®
Storage	Temperature-controlled and monitored conditions at 2 to 8°C in a secure storage area at the site
Dosage form	Liquid, ready-to-use 20% IgG solution stabilized with 250 mmol/L L-proline and 20 mg/L polysorbate 80

IgG = immunoglobulin G.

IgPro20 for SC administration will be provided as a 20% IgG solution in a vial containing 10 g IgG in a 50 mL volume. IgPro20 will be manufactured by CSLB, in accordance with ICH GMP guidelines and local regulatory requirements.

Information on the preparation and SC administration of IgPro20 is provided in the IMP manual.

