**Table 5** **Investigational Medicinal Product Dosing Characteristics**

SC Infusion Parameter	IgPro20	Placebo
Route	SC	SC
Anatomical location	Abdomen, thigh, upper arm, and/or lateral hip	Abdomen, thigh, upper arm, and/or lateral hip
Total infusion volume	Dependent on body weight (eg, 80 kg subject, 200 mL)	Dependent on body weight (eg, 80 kg subject, 200 mL)
Infusion duration	Volume and number of infusion sites dependent	Volume and number of infusion sites dependent

SC = subcutaneous.

All IMP in the study will be administered by SC infusions as weekly doses of 0.5 g/kg. At least the first SC infusion for Week 1 and Week 2 must be administered during the study visit at the investigational site to allow for training and confirmation of appropriate SC infusion technique. After Week 1 and Week 2, all weekly SC infusions will be self-administered at home. The SC infusions can be performed on 1, 2, 3, or 4 days each week and more than 1 infusion can be performed on a single day. It is preferred that the SC infusions be performed in a similar way throughout the study, ie, the same number of infusions and the same number of days each week after Week 2; however, the dosing regimen can be adjusted during the study in case of intolerance or inconvenience. All SC infusions for the previous week must be performed before the following study visit, eg, all Week 4 SC infusions performed before the day of the Week 5 Visit. Body weight will be measured at every study visit and changes in body weight > 2 kg will require a dose volume adjustment. The total dosing volume of IMP will be managed by the interactive response technology (IRT) system. Preparation instructions are provided in the IMP manual.

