### 8.1.4 Pharmacokinetic Assessments

Trough serum samples for IgG level determination will be collected at Screening and at specified study visits (Table 12).

Additional blood samples for rich PK sampling of IgG levels will be collected at Week 37 (Study Period 2). Rich PK samples will be collected from up to 10 Japanese subjects and 30 non-Japanese subjects. The Week 37, 168-hour rich PK blood sample must be drawn before start of Week 38 dose infusion. The additional samples will be collected at the times listed in [Table 14](#). Blood draws for rich PK samples may be drawn by a phlebotomist at the subject's home where available and/or allowed by local law.

The samples for serum IgG concentrations will be analyzed by the central laboratory by immunoturbidimetry. Serum IgG levels will not be disclosed to the investigative site or any blinded study personnel prior to unblinding the study. See [Schedule of Assessments for Rich Pharmacokinetic Sampling](#) for details.

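### Apparent clearance is to be derived from uncorrected total serum IgG at Week 37, so it is too low by the share of that IgG that is the subject's own

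*SAP*

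**What the plan says.** The active substance is "Human normal IgG" (Protocol Section 5.1.1), which is the same analyte that subjects produce themselves. On the assay, Protocol Section 8.1.4 says: "The samples for serum IgG concentrations will be analyzed by the central laboratory by immunoturbidimetry". Neither document describes a way to tell infused IgG from own IgG.

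SAP Section 12.2 lists AUC over the dosing interval, Ctrough, Cmax, Tmax, an entry described as "Apparent clearance at steady state", and Vz,ss/F. It then limits the input: "Only concentrations from rich PK sampling will be used to calculate the PK parameters based on the PK analysis set". Rich sampling takes place only at Week 37, with a trough and then samples at 24, 48, 72, 120 and 168 hours (Protocol Table 14). Results are to be grouped by dosing regimen and by Japan versus non-Japan.

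Serum IgG is also measured before any IgPro20 is given: at Screening, at Baseline and, for Sequence B, at Week 25 before the switch from placebo. SAP Section 12.1 gives samples outside the rich set only descriptive summaries, kept apart from the rich PK summaries. Neither document mentions subtracting a baseline. SAP Section 12 refers non-compartmental work to an internal guideline, PK-GDL-01, whose content is not reproduced.

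Protocol Section 10.4.4.1 names only Cmax, Ctrough and AUC. The SAP modification history shows that clearance and volume were added in version 5.

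**The concern.** At steady state, dose over AUC for one dosing interval is an apparent clearance only if the whole AUC comes from the dose. Here part of it is IgG that the subject makes. The quoted sentence leaves no pre-treatment sample in the derivation with which to remove that part.

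Two things follow. The reported CLss/F would not be the clearance of IgPro20. It would also vary with each subject's own IgG, so two groups that handle the drug identically could show different values. That matters because the table is split by region and regimen in a small sample (up to 10 Japanese and 30 non-Japanese subjects), where a difference could be read as one in drug handling.

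Vz,ss/F has the same weakness. On the usual formula it is CLss/F divided by the terminal slope, and a constant own-IgG level lowers the first and flattens the second. These errors pull in opposite directions and can partly cancel, so no size or direction is claimed for Vz,ss/F.

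**Working it through.** **Inputs from the documents**
- Weekly dose 0.5 g/kg (Protocol Section 5.1.3). The 80 kg example agrees: 200 mL × 0.2 g/mL = 40 g, and 40/80 = 0.5 g/kg.
- Dosing interval 7 days (SAP Section 12.2).
- Predicted median average IgG (Protocol Section 3.3.2): it "was comparable following 2 g/kg monthly IVIG (22.20 g/L) and 0.5 g/kg weekly SCIG (20.85 g/L), after 8 to 10 weeks". The model parameters are not given, so 20.85 g/L cannot be reproduced. The text does not say whether it is total or infused IgG.
- Predicted IV trough 13.15 g/L (same section).

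**Assumed:** own-IgG level b of 7, 10 or 12 g/L. Neither document gives a level or a range.

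**Formula.** CLss/F = Dose/AUC, with AUC = Cavg × 7 days. If own IgG is constant at b, then AUC(total) = AUC(infused) + 7b. So CL(uncorrected)/CL(true) = (Cavg,total − b)/Cavg,total, and the relative error is −b/Cavg,total. It is negative for any b above zero.

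**Reading A: 20.85 g/L is total IgG.** Uncorrected CLss/F = 0.5/(20.85 × 7) = 0.5/145.95 = 3.43 mL/kg/day.

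**Reading B: 20.85 g/L is infused IgG only.** Total is then 20.85 + b, and the true CLss/F is 3.43 mL/kg/day.

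| b (g/L, assumed) | A: corrected CLss/F (mL/kg/day) | A: error | B: uncorrected CLss/F (mL/kg/day) | B: error |
|---|---|---|---|---|
| 7 | 0.5/(13.85 × 7) = 5.16 | −7/20.85 = −34% | 2.56 | −7/27.85 = −25% |
| 10 | 0.5/(10.85 × 7) = 6.58 | −48% | 2.32 | −10/30.85 = −32% |
| 12 | 0.5/(8.85 × 7) = 8.07 | −58% | 2.17 | −12/32.85 = −37% |

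On Reading A, own IgG cannot exceed the predicted IV trough, which caps the error near 13.15/20.85 = 63%.

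**If own IgG falls on treatment.** On Reading A, with total IgG held at 20.85 g/L and own IgG at Week 37 reduced by 25% (assumed), b of 7 to 12 g/L gives 25 to 43% too low. A fall of 50% gives 17 to 29%.

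**Check on the planned sampling times.** A one-compartment SC profile (assumed absorption rate 0.3 per day, half-life 20 days), sampled at the six planned times and integrated by the linear-up, log-down rule, gave errors of −33.5%, −47.9% and −57.5% for b = 7, 10 and 12 g/L, and +0.2% for b = 0. This shows that the sampling and the trapezoidal rule reproduce the formula. It is not separate evidence for the size of b.

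**Spurious group difference.** Take two groups with the same infused average of 10.85 g/L (true CLss/F 6.58 in both) and assumed own IgG of 8 and 12 g/L. The planned values are 0.5/(18.85 × 7) = 3.79 and 0.5/(22.85 × 7) = 3.13 mL/kg/day. The second is about 17.5% lower (18.85/22.85 = 0.825) with no difference in drug handling.

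**The case against.** The strongest reply has four parts.

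First, PK-GDL-01 governs the non-compartmental work and might already define a correction for endogenous analytes. We cannot see it, so this stays open. But a correction using a Baseline or Week 25 sample would conflict with the sentence that admits rich samples only, so the SAP wording needs reconciling either way.

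Second, the stated objective is the pharmacokinetics of IgG at Week 37 (Protocol Section 2.3.1), not of infused IgG alone. This stands for AUC, Cmax and Ctrough, which are valid as total-IgG exposure and need no second corrected set. It does not rescue a clearance, which divides the administered dose by an AUC that the dose only partly produced.

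Third, the consequence is small. The PK results are exploratory and purely descriptive (SAP Section 12.3), and serum IgG by visit and region is summarized elsewhere, so a difference in starting IgG could be noticed. That limits the weight of the point without making the parameter right.

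Fourth, baseline subtraction has its own assumption. If own IgG falls on treatment, or if Baseline still contains earlier therapeutic IgG, subtraction over-corrects. This stands and is the reason to report both versions.

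A reader might also infer that the documents show clearance to be 30 to 60% too low. They do not. On Reading A that range needs own IgG of about 6.3 to 12.5 g/L, unchanged at Week 37. Nor do the documents state that subjects have normal IgG levels. The direction of the error does not depend on that, but its size does.

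**Conclusion.** The point holds for CLss/F and, without a stated size, for Vz,ss/F. As written, SAP Section 12.2 gives a CLss/F that is too low by b/Cavg,total for any own-IgG level above zero, and its regional and regimen summaries cannot separate own-IgG level from drug handling.

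Only the direction and the formula follow from the documents. The percentages rest on an assumed b of 7 to 12 g/L, on whether 20.85 g/L is total IgG (34 to 58%) or infused IgG only (25 to 37%), and on own IgG being stable on treatment. A fall in own IgG makes the error smaller.

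A reader might take this further, as a fault in the total-IgG exposure measures or in the dose rationale. Neither follows: the first are what they are labelled to be, and the second does not use CLss/F. No efficacy or safety test is affected. This is an inexpensive correction to an exploratory table.

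**What to change.** In SAP Section 12.2:

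- Derive CLss/F and Vz,ss/F from baseline-corrected concentrations, meaning each rich-PK value minus the subject's serum IgG before any IgPro20. Use Baseline for Sequence A and the pre-switch Week 25 value for Sequence B.
- Amend the sentence that admits rich samples only so that it allows this one extra sample, and reconcile it with PK-GDL-01.
- Report the uncorrected CLss/F and Vz,ss/F beside the corrected ones, labelled as total-IgG parameters. Keep AUC, Cmax and Ctrough as total IgG.
- Summarize the corrected values with and without Sequence A subjects who had IgG within 2 months before Baseline. Exclusion criterion 9 admits such subjects if they deteriorated after stopping, so their Baseline may include residual therapeutic IgG.

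The cost is SAP wording and one additional PK table, with no new samples or visits. The drawback is the assumption that own IgG stays stable on treatment. If it falls, but not to zero, the uncorrected CLss/F is too low and the corrected one too high, so the two together bracket the true value.

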## 12.3 Pharmacokinetics Statistical Analyses

No statistical analysis except the summary statistics described above will be performed.

## 14 Appendices

### 14.1 Simulation Report for Sample Size Estimation

This report is to describe the details of the simulation performed for the sample size estimation in the IgPro20\_3007 study, including assumptions and scenarios, as well as the simulation code.

#### 14.1.1 Primary Endpoint

The derivation of the primary endpoint takes into account of the following information:

- TIS assessments at the three visits Week 17, 21, and 25
- Withdrawn from IMP or study or receiving oral rescue corticosteroid treatment.

It is expected that the TIS assessments at the three visits are correlated. In addition, once a subject is withdrawn from IMP or study, or receiving oral rescue corticosteroid treatment, the subject is considered not showing response at that visit and at all subsequent visits. Therefore, the probability for a subject showing response (TIS  $\geq 20$  points) at one visit is conditional on the response status of the subject (including TIS, withdrawn from IMP or study, receiving oral rescue corticosteroid treatment) at the previous visit.

#### 14.1.2 Assumptions

The assumptions used in the simulation are tabulated in [Table 3](#) in the SAP Section [4.5](#). With the probability of having a TIS  $\geq 20$  points being specified, the probability of showing no response, including TIS  $< 20$  points, or withdrawn from IMP or study, or receive oral rescue corticosteroid treatment, is the complement. For example, it is assumed that the probability of having a TIS  $\geq 20$  points at Week 17 is 65% in Treatment Sequence A, then the probability of having TIS  $< 20$  points at Week 17 in Treatment Sequence A, being withdrawn from IMP or study, receive oral rescue corticosteroid treatment combined, is 35%.

#### 14.1.3 Scenario

The total sample size investigated cover the range of (116, 130) and the conditional probability of having a TIS  $\geq 20$  points given the subject showing response at the previous visit in the range of (0.85, 0.95). Each scenario investigated was simulated 5000 times.

**Table 14: Results of Sample Size Simulation**

Total sample size	Probability of TIS $\geq 20$ conditional on showing a response at the previous visit	Power	Estimated median responder rate in Treatment Sequence A	Estimated median responder rate in Treatment Sequence B
116	0.95	0.914	0.655	0.345
	0.9	0.855	0.603	0.310
	0.85	0.784	0.552	0.276
118	0.95	0.925	0.661	0.339
	0.9	0.869	0.610	0.305
	0.85	0.806	0.542	0.271
120	0.95	0.933	0.667	0.333
	0.9	0.878	0.600	0.300
	0.85	0.817	0.550	0.283
122	0.95	0.932	0.656	0.344
	0.9	0.882	0.607	0.311
	0.85	0.821	0.557	0.279
124	0.95	0.939	0.661	0.339
	0.9	0.895	0.597	0.306
	0.85	0.833	0.548	0.274
126	0.95	0.948	0.667	0.333
	0.9	0.905	0.603	0.317
	0.85	0.839	0.556	0.286
128	0.95	0.934	0.656	0.344
	0.9	0.887	0.609	0.313
	0.85	0.844	0.547	0.281
130	0.95	0.940	0.662	0.338
	0.9	0.897	0.600	0.308
	0.85	0.847	0.554	0.277

The total sample size of 126 subjects is selected as the minimum sample size for a power of  $\geq 90\%$  based on the above assumptions.

**14.1.4 Simulation code (in R, version 3.4.2)**

```

library(exact2x2)
##data simulation
r_act=0.65    ##response rate at W17, active arm (treatment sequence A)
r_pbo=0.30    ##response rate at W17, placebo arm (treatment sequence B)
cond_p_nonres_act=0.2
cond_p_nonres_pbo=0.1

single_set=function(N,r_act,r_pbo,cond_p_res,cond_p_nonres_act,
cond_p_nonres_pbo) {

subj=seq(1,N)
trt=c(rep("act",times=N/2), rep("pbo", times=N/2))
wk17=c(rbinom(N/2, 1, r_act), rbinom(N/2, 1, r_pbo))
wk21_act=rbinom(N/2,1,cond_p_res)*(wk17[1:(N/2)]==1)+rbinom(N/2,1,
cond_p_nonres_act)*(wk17[1:(N/2)]==0)
wk21_pbo=rbinom(N/2,1,cond_p_res)*(wk17[(N/2+1):N]==1)+rbinom(N/2,1,
cond_p_nonres_pbo)*(wk17[(N/2+1):N]==0)
wk21=c(wk21_act, wk21_pbo)
wk25_act=rbinom(N/2,1,cond_p_res)*(wk21[1:(N/2)]==1)+rbinom(N/2,1,
cond_p_nonres_act)*(wk21[1:(N/2)]==0)
wk25_pbo=rbinom(N/2,1,cond_p_res)*(wk21[(N/2+1):N]==1)+rbinom(N/2,1,
cond_p_nonres_pbo)*(wk21[(N/2+1):N]==0)
wk25=c(wk25_act, wk25_pbo)

responses=wk17+wk21
responder=(responses>0)*(wk25>0)+0

nres_act=sum(responder[1:(N/2)])
nres_pbo=sum(responder[(1+N/2):N])
tbl=matrix(c(nres_act, N/2-nres_act, nres_pbo, N/2-nres_pbo), 2, 2)
return(c(fisher.test(tbl,      alternative="greater")$p.value,      2*nres_act/N,
2*nres_pbo/N))
}

N_RANGE=rep(seq(116, 130, by=2), each=3)
PROB_CON=rep(c(0.95, 0.9, 0.85), 8)
power=rep(-1, 24)
median_rate_a=rep(-1, 24)
median_rate_p=rep(-1, 24)

ALL=cbind(N_RANGE, PROB_CON, power, median_rate_a, median_rate_p)
for (k in 1:24){
  N=ALL[k,1]
  cond_p_res=ALL[k,2]
  set.seed(12345)
  result=matrix(-1,ncol=3,nrow=5000)

  for (i in 1:nrow(result))

```

```
{result[i,]=single_set(N,r_act,r_pbo,cond_p_res,cond_p_nonres_act,cond_p_nonres_pbo) }

  ALL[k, 3]=sum(result[,1]<0.025)/nrow(result)  ##power 85.54%
  ALL[k, 4]=median(result[,2])    ##median of responder rate in active arm
  ALL[k, 5]=median(result[,3])    ##median of responder rate in pbo arm
}

ALL

write.csv(ALL,  "H:/Projects/IgPro20_3007/Stats  Technical/Sample  Size/Design
Dec2018/all.csv")
```

The results have been re-programmed independently in SAS (version 9.4) which confirmed the power calculation with less than 1.2% difference.

